3.4.5 Immunogenicity Assessments

Blood samples for immunogenicity assessments will be collected at the time points indicated in the Schedule of Events for each study part, [Table 9](#) for the blinded Part A, and [Table 10](#), [Table 11](#) and [Table 12](#) for open-label Part B, and [Table 12](#) for Part C. On Day 1 and Day 29 ([Table 9](#)), and on OL-Day 1 ([Table 12](#)) and on OL-Day 1 and OL-Day 29 ([Table 11](#)), blood samples for immunogenicity assessment will be collected before administration of vaccine. The following analytes will be measured:

- Serum bAb level against SARS-CoV-2 as measured by enzyme-linked immunosorbent assay (ELISA) specific to the SARS-CoV-2 S protein

- Serum nAb titer against SARS-CoV-2 as measured by pseudovirus and/or live virus neutralization assays

In Part C, serum samples for immunogenicity assessment will be analyzed for the following:

- Serum nAb against SARS-CoV-2 as measured by pseudovirus (and/or live virus) using the B.1.351 and the D614G variant sequences of SARS-CoV-2 S protein (and/or variant strains)
- Serum bAb against SARS-CoV-2 as measured by ELISA against the B.1.351 and the D614G variant sequences of SARS-CoV-2 S protein

Sample aliquots will be designed to ensure that backup samples are available and that adequate vial volumes may allow further testing needs. The actual time and date of each sample collected will be recorded in the eCRF, and unique sample identification will be utilized to maintain the blind at the laboratory at all times and to allow for automated sample tracking and housing. Handling and preparation of the samples for analysis, as well as shipping and storage requirements, will be provided in a separate study manual.

The ELISA and measurement of nAb titers will be performed in a laboratory designated by the Sponsor.

For participants who provide consent ([Section 5.3](#)), serum from immunogenicity testing may be used for future research, which may be performed at the discretion of the Sponsor to further characterize the immune response to SARS-CoV-2, additional assay development, and the immune response across the coronaviruses.

3.4.6 Blood Sampling Volumes

In Part A, the maximum planned volumes of blood sampled per participant are 66 mL for 1 day, 182 mL for 28 days, and 398 mL for the complete study ([Table 4](#)).

Table 4: Maximum Blood Sampling Volumes per Participant by Visit (Part A, Blinded)

Study Visit Day	D0	D1	D15	D29	D43	D57	D209	D394	Total
Safety laboratory tests	16 mL			16 ¹ mL		16 ¹ mL			48 mL
Immunogenicity assays		50 mL	50 mL	50 mL	50 mL	50 mL	50 mL	50 mL	350 mL
Total	16 mL	50 mL	50 mL	66 mL	50 mL	66 mL	50 mL	50 mL	398 mL

Abbreviation: D = Day.

¹Only participants in Cohort 2 will have blood sampled for safety laboratory tests at Day 29 and Day 57.

In Parts B and C, the maximum planned volumes of blood sampled per participant are 20 mL per visit, 80 mL for 28 days, and a total of 120 mL (Table 5).

Table 5: Maximum Blood Sampling Volumes per Participant by Visit (Part B and Part C Open-label)

Study Visit Day	OL-D1	OL-D8	OL-D15	OL-D29	OL-D57	OL-M6-7 ¹	Total
Immunogenicity assays	20 mL	20 mL	20 mL	20 mL	20 mL	20 mL	120 mL

Abbreviation: OL = Open-Label; D = Day; M = month.

¹ OL-M6-7 is calculated based on the participant's last vaccination day, ie, for participants receiving a single booster dose this will be OL-M6, and for participants; who receive 2 injections, this visit will be based off of the day of second injection (ie, OL-Day 29), and will be OL-M7. In Part C, the last blood sample collection will be at OL-M6.

3.4.7 Safety Assessments

In Part A (blinded), Part B (open-label), and Part C (open-label), safety assessments will include monitoring and recording of the following for each participant:

- Solicited local and systemic ARs (Section 3.4.8.4) that occur during the 7 days following each injection (ie, the day of injection and 6 subsequent days). Solicited ARs will be recorded daily using eDiaries (Section 3.4.2).
- Unsolicited AEs observed or reported during the 28 days following each injection (ie, the day of injection and 27 subsequent days). Unsolicited AEs are AEs that are not included in the protocol-defined solicited ARs (Section 3.4.8.4).
- AEs leading to discontinuation from dosing and/or study participation from Day 1 through Day 394 (Part A), OL-Month 6 or 7 (Part B), and OL-Month 6 (Part C) or withdrawal from the study.
- MAAEs from Day 1 through Day 394 (Part A), OL-Month 6 or 7 (Part B), and OL-Month 6 (Part C) or withdrawal from the study.

- SAEs from Day 1 through Day 394 (Part A), OL-Month 6 or 7 (Part B), and OL-Month 6 (Part C) or withdrawal from the study.
- Results of safety laboratory tests (Part A).
- Vital sign measurements.
- Physical examination findings.
- Assessments for SARS-CoV-2 infection from Day 1 through study completion ([Section 3.4.1](#)).

3.4.8 Safety Definitions

3.4.8.1 Adverse Event

An AE is defined as any untoward medical occurrence associated with the use of a drug in humans, whether or not considered drug related.

A treatment-emergent AE (TEAE) is defined as any event not present before exposure to vaccine or any event already present that worsens in intensity or frequency after exposure.

Events Meeting the Adverse Event Definition

- Any abnormal laboratory test result (hematology, clinical chemistry, or PT/PTT) or other safety assessment (eg, electrocardiogram, radiological scan, vital sign measurement), including one that worsens from baseline and is considered clinically significant in the medical and scientific judgment of the investigator.
- Exacerbation of a chronic or intermittent pre-existing condition including either an increase in frequency and/or intensity of the condition.
- New conditions detected or diagnosed after mRNA-1273 vaccine administration even though it may have been present before the start of the study.

Events NOT Meeting the Adverse Event Definition

- Medical or surgical procedure (eg, endoscopy, appendectomy): the condition that leads to the procedure is the AE.
- Situations in which an untoward medical occurrence did not occur (social and/or convenience admission to a hospital).

An AR is any AE for which there is a reasonable possibility that the investigational product caused the AE ([Section 3.4.8.4](#)). For the purposes of investigational new drug safety reporting,

“reasonable possibility” means that there is evidence to suggest a causal relationship between the investigational product and the AE.

An unsolicited AE is any AE reported by the participant that is not specified as a solicited AR in the protocol or is specified as a solicited AR in the protocol but starts outside the protocol-defined post-injection period for reporting solicited ARs (ie, for the 7 days after each injection).

3.4.8.2 Medically Attended Adverse Event

An MAAE is an AE that leads to an unscheduled visit to a healthcare practitioner (HCP). This would include visits to a study site for unscheduled assessments (eg, rash assessment, abnormal laboratory follow-up, SARS-CoV-2 infection [[Section 3.4.1](#)]) and visits to HCPs external to the study site (eg, urgent care, primary care physician). Investigators will review unsolicited AEs for the occurrence of any MAAEs. All MAAEs must be fully reported on the MAAE page of the eCRF.

3.4.8.3 Serious Adverse Event

An AE (including an AR) is considered an SAE if, in the view of either the investigator or Sponsor, it results in any of the following outcomes:

- Death
A death that occurs during the study or that comes to the attention of the investigator during the protocol-defined follow-up period must be reported to the Sponsor, whether or not it is considered related to study vaccine.
- Is life-threatening
An AE is considered life-threatening if, in the view of either the investigator or the Sponsor, its occurrence places the participant at immediate risk of death. It does not include an AE that, had it occurred in a more severe form, might have caused death.
- Inpatient hospitalization or prolongation of existing hospitalization
In general, inpatient hospitalization indicates the participant was admitted to the hospital or emergency ward for at least one overnight stay for observation and/or treatment that would not have been appropriate in the physician’s office or outpatient setting. The hospital or emergency ward admission should be considered an SAE regardless of whether opinions differ as to the necessity of the admission. Complications that occur during inpatient hospitalization will be recorded as an AE; however, if a complication/AE prolongs hospitalization or otherwise fulfills SAE criteria, the complication/AE will be recorded as a separate SAE.

- Persistent or significant incapacity or substantial disruption of the ability to conduct normal life functions
This definition is not intended to include experiences of relatively minor medical significance such as uncomplicated headache, nausea/vomiting, diarrhea, influenza, and accidental trauma (eg, sprained ankle) which may interfere with or prevent everyday life functions but do not constitute a substantial disruption.
- Congenital anomaly or birth defect
- Medically important event
Medical judgment should be exercised in deciding whether SAE reporting is appropriate in other situations, such as important medical events that may not be immediately life-threatening or result in death or hospitalization but may jeopardize the participant or require medical or surgical intervention to prevent one of the other outcomes listed in the above definition. These events should usually be considered serious. Examples of such medical events include allergic bronchospasm requiring intensive treatment in an emergency room or at home, blood dyscrasias or convulsions that do not result in inpatient hospitalization, or the development of drug dependency or drug abuse.

3.4.8.4 Solicited Adverse Reactions

The term “reactogenicity” refers to the occurrence and intensity of selected signs and symptoms (ARs) occurring after vaccine administration. The eDiary ([Section 3.4.2](#)) will solicit participant reporting of ARs using a structured checklist. Participants will record such occurrences in an eDiary on the day of each vaccine administration and for the 6 days after a day of injection.

The following local ARs will be solicited by the eDiary: pain at injection site, erythema (redness) at injection site, swelling/induration (hardness) at injection site, and localized axillary swelling or tenderness ipsilateral to the injection arm.

The following systemic ARs will be solicited by the eDiary: headache, fatigue, myalgia (muscle aches all over the body), arthralgia (aching in several joints), nausea/vomiting, rash, body temperature (potentially fever), and chills.

The study site staff will contact the participant within 24 hours of becoming aware of the event if any of the following occurs within 7 days after study injection:

- Severe (Grade 3) local or systemic ARs ([Table 6](#))
- Presence of any rash

The purpose of the contact is to assess the nature of AR, including assessment of potential pause rules. In the event that rash is reported, the participant will be asked to return to the study site for assessment by the investigator.

The investigator will review, confirm, and grade reactogenicity according to the grading scales presented in [Table 6](#), modified from the Toxicity Grading Scale for Healthy Adult and Adolescent Volunteers Enrolled in Preventive Vaccine Clinical Trials ([DHHS 2007](#)).

If a solicited local or systemic AR continues beyond 7 days after injection, the participant will be prompted to capture solicited local or systemic ARs in the eDiary until resolution. Adverse reactions recorded in eDiaries beyond Day 7 should be reviewed either via telephone call or at the following study visit. All solicited ARs (local and systemic) will be considered causally related to injection.

Table 6: Solicited Adverse Reactions and Grades

Reaction	Grade 0	Grade 1	Grade 2	Grade 3	Grade 4*
Injection site pain	None	Does not interfere with activity	Repeated use of over-the-counter pain reliever > 24 hours or interferes with activity	Any use of prescription pain reliever or prevents daily activity	Requires emergency room visit or hospitalization
Injection site erythema (redness)	< 25 mm/ < 2.5 cm	25 - 50 mm/ 2.5 - 5 cm	51 - 100 mm/ 5.1 - 10 cm	> 100 mm/ > 10 cm	Necrosis or exfoliative dermatitis
Injection site swelling/induration (hardness)	< 25 mm/ < 2.5 cm	25 - 50 mm/ 2.5 - 5 cm	51 - 100 mm/ 5.1 - 10 cm	> 100 mm/ > 10 cm	Necrosis
Axillary (underarm) swelling or tenderness ipsilateral to the side of injection	None	No interference with activity	Repeated use of over-the-counter (non-narcotic) pain reliever > 24 hours or some interference with activity	Any use of prescription (narcotic) pain reliever or prevents daily activity	Requires emergency room visit or hospitalization
Headache	None	No interference with activity	Repeated use of over-the-counter pain reliever > 24 hours or some interference with activity	Significant; any use of prescription pain reliever or prevents daily activity	Requires emergency room visit or hospitalization
Fatigue	None	No interference with activity	Some interference with activity	Significant; prevents daily activity	Requires emergency room visit or hospitalization
Myalgia (muscle aches all over body)	None	No interference with activity	Some interference with activity	Significant; prevents daily activity	Requires emergency room visit or hospitalization
Arthralgia (joint aches in several joints)	None	No interference with activity	Some interference with activity	Significant; prevents daily activity	Requires emergency room visit or hospitalization

Reaction	Grade 0	Grade 1	Grade 2	Grade 3	Grade 4*
Nausea/vomiting	None	No interference with activity or 1-2 episodes/24 hours	Some interference with activity or > 2 episodes/24 hours	Prevents daily activity, requires outpatient intravenous hydration	Requires emergency room visit or hospitalization for hypotensive shock
Chills	None	No interference with activity	Some interference with activity not requiring medical intervention	Prevents daily activity and requires medical intervention	Requires emergency room visit or hospitalization
Fever (oral)	< 38.0°C < 100.4°F	38.0 – 38.4°C 100.4 – 101.1°F	38.5 – 38.9°C 101.2 – 102.0°F	39.0 – 40.0°C 102.1 – 104.0°F	> 40.0°C > 104.0°F
Rash*	No rash	Localized rash, without associated symptoms	Maculopapular rash, covering < 50% body surface area	Generalized urticarial, covering > 50% body surface area	Generalized exfoliative, ulcerative or bullous dermatitis, eg, Stevens-Johnson syndrome or erythema multiforme

* Grading for rash and Grade 4 events per Investigator assessment (with exception of fever).

Sources: Guidance for Industry – Toxicity Grading Scale for Healthy Adult and Adolescent Volunteers Enrolled in Preventive Vaccine Clinical Trials; tables for clinical abnormalities (DHHS 2007). Division of AIDS Grading the Severity of Adult and Pediatric Adverse Events (DHHS 2014).

In case of any rash episode observed within 7 days after study injection, the participant will be instructed to contact the study site within 24 hours. During participant evaluation, the investigator should categorize the rash as one of the following:

- Rash no longer present and history not consistent with urticaria.
- Rash no longer present but history is consistent with urticaria.
- Rash present but clinical findings are not consistent with urticaria. Alternative diagnosis should be specified as an AE.
- Rash present and clinical findings consistent with urticaria.

Any solicited AR that meets any of the following criteria must be entered into the participant's source document and must also be recorded as an AE in the participant's Adverse Event eCRF:

- Solicited local or systemic AR that results in a visit to an HCP (MAAE)
- Solicited local or systemic AR leading to the participant withdrawing from the study or the participant being withdrawn from the study by the investigator (AE leading to withdrawal)
- Solicited local or systemic AR lasting beyond 7 days post-injection
- Solicited local or systemic AR that leads to participant withdrawal from vaccine administration
- Solicited local or systemic AR that otherwise meets the definition of an SAE
- Solicited AR with a toxicity score of Grade 3 or greater

An unsolicited AE is any AE reported by the participant that is either not specified as a solicited AR in the protocol or is specified as a solicited AR in the protocol, but starts outside the protocol-defined post-injection period for reporting solicited ARs (ie, for the 7 days after each injection).

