3.2.5 Participant Withdrawal From Study Dosing

Every reasonable attempt will be made to follow up with participants for safety throughout the entire study period, even if further injection is withheld or the participant misses one or more visits.

Unless consent is withdrawn, a participant who withdraws or is withheld from receiving the second dose of study vaccine will remain in the study and complete all scheduled visits and assessments.

The investigator, in consultation with the Sponsor's medical monitor, may withhold a participant from further injection if the participant experiences any of the following:

- Becomes pregnant
- Develops, during the course of the study, symptoms or conditions listed in the exclusion criteria ([Section 3.1.7](#))
- Experiences an AE (other than reactogenicity) after injection that is considered by the investigator to be related to investigational product ([Section 3.4.8.10](#)) and is of Grade 3 (severe) or greater severity ([Appendix 2](#))
- Experiences an AE or SAE that, in the judgment of the investigator, requires study vaccine withdrawal due to its nature, severity, or required treatment, regardless of the causal relationship to vaccine
- Experiences a clinically significant change in clinical laboratory test results, vital sign measurements, or general condition that, in the judgment of the investigator, requires vaccine withdrawal
- Experiences anaphylaxis clearly attributed to study vaccine
- Experiences generalized urticaria related to the study vaccine

The reason(s) for withdrawal from further injection will be recorded.

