3.4.8.9 Assessment of Severity

An event is defined as “serious” when it meets at least one of the predefined outcomes as described in the definition of an SAE ([Section 3.4.8.3](#)), NOT when it is rated as severe.

The severity (or intensity) of an AR or AE refers to the extent to which it affects the participant’s daily activities and will be classified as mild (Grade 1), moderate (Grade 2), severe (Grade 3), or Grade 4 using the following criteria:

- Mild (Grade 1): These events do not interfere with the participant’s daily activities.
- Moderate (Grade 2): These events cause some interference with the participant’s daily activities but do not require medical intervention.
- Severe (Grade 3): These events prevent the participant’s daily activity and require medical intervention.
- Grade 4 (solicited ARs): These events require an emergency room visit or hospitalization.

Changes in the severity of an AE should be documented to allow an assessment of the duration of the event at each level of intensity to be performed. An AE characterized as intermittent requires documentation of onset and duration of each episode.

The Toxicity Grading Scale for Healthy Adult and Adolescent Volunteers Enrolled in Preventive Vaccine Clinical Trials ([DHHS 2007](#)) will be used to categorize local and systemic solicited ARs ([Table 6](#)), clinical laboratory test results, and vital sign measurements observed during this study. Specific criteria for clinical and laboratory abnormalities are presented in [Appendix 2](#) ([Table 13](#) and [Table 14](#), respectively) and will be graded if outside of the reference range for the laboratory utilized.

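### The 24-hour reactogenicity contact rule names Grade 3 reactions and any rash; read literally, it leaves out other Grade 4 reactions, mainly fever above 40.0 °C

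*Protocol*

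**What the plan says.** Protocol section 3.4.8.4 sets a participant contact "within 24 hours of becoming aware of the event if any of the following occurs within 7 days after study injection". There are two triggers. The first is "Severe (Grade 3) local or systemic ARs", with a pointer to Table 6; the second is rash of any grade. The stated purpose is to establish the nature of the reaction, "including assessment of potential pause rules".

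Table 6 grades each solicited reaction from 0 to 4. Fever of 39.0 to 40.0 °C is Grade 3. Grade 4 fever is "> 40.0°C > 104.0°F". The table footnote says who assigns the top grade: "Grading for rash and Grade 4 events per Investigator assessment (with exception of fever".

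Section 3.4.8.9 labels Grade 3 as severe and gives Grade 4 its own entry: "severe (Grade 3), or Grade 4 using the following criteria". Later in section 3.4.8.4, the list of solicited reactions that must also be entered on the adverse event eCRF includes "Solicited AR with a toxicity score of Grade 3 or greater".

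In section 3.3.2.1, Table 3, pause criterion 2 covers SAEs and Grade 4 AEs not reasonably attributable to a cause other than the injection, with a threshold of 3 participants. The pause rules bind in Part A only. In Parts B and C the same events are still monitored and passed to the Sponsor and the Safety Monitoring Committee.

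**The concern.** A safety instruction that escalates on severity should apply at its threshold and above. This one names a single grade. Since the protocol treats severe and Grade 4 as different classes, the word severe in the bullet does not bring Grade 4 in. A site that follows the text exactly would owe a prompt contact to a participant with a fever of 40.0 °C and not to one with 40.1 °C.

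The omission also sits badly with the purpose of the contact. It is supposed to feed pause-rule assessment, and the only grade that the pause criteria name is Grade 4. What is at stake is a prompt check on the participant and early information for safety oversight, not the analysis.

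**Working it through.** The plan gives no figure to reproduce. The check compares the texts and counts the reactions.

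**1. Which Grade 4 reactions are not named?** Table 6 lists 4 local and 8 systemic reactions: 4 + 8 = 12. Rash triggers contact at every grade, which leaves 12 − 1 = 11 whose Grade 4 level is not named.

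**2. For how many does the omission have a practical effect?** By the Table 6 footnote, Grade 4 is assigned by the investigator for all of these except fever: 11 − 1 = 10. Of the 10, 8 are defined at Grade 4 by an emergency room visit or hospitalization (injection-site pain, axillary swelling or tenderness, headache, fatigue, myalgia, arthralgia, nausea/vomiting, chills). The other 2 are defined by tissue damage at the injection site (erythema, swelling/induration). Once one of these has been graded 4, the investigator is already involved. That leaves 11 − 10 = 1, fever, which is graded from the thermometer reading alone.

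**3. Where is the boundary?** 40.0 °C is Grade 3 and triggers contact. 40.1 °C is Grade 4 and, literally, does not. The difference is 40.1 − 40.0 = 0.1 °C. Section 3.4.2 asks for only the highest temperature of the day, so a day that peaks at 40.1 °C leaves no Grade 3 fever entry for that day.

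**4. Does another provision supply the missing contact?**

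| Protocol section | What it requires | Timed reactogenicity contact for Grade 4? |
|---|---|---|
| 3.3.2.1 | 24-hour report to the Sponsor of events that may meet a pause criterion | No; it is a report to the Sponsor |
| 3.4 | Unscheduled visits may be prompted by reactogenicity | No; permitted, not required |
| 3.4.1 | Illness visit or consultation within 24 hours or as soon as possible for CDC-defined symptoms | No; its purpose is a swab, and the symptom list is cited but not reproduced |
| 3.4.2 | Telephone follow-up when an eDiary record shows relevant safety events | No; a call is required but no time limit is set |
| 3.4.8.4 | eCRF entry for Grade 3 or greater | No; it concerns recording |
| 3.4.8.8 | 24-hour SAE report to the Sponsor | No; it is a report to the Sponsor, and a fever reading alone is not an SAE criterion |
| 3.4.8.11 | Follow-up to resolution or stability | No; untimed |

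**5. What was intended?** The closest parallel is the eCRF rule in section 3.4.8.4, which concerns the same solicited reactions and uses the inclusive threshold. With the pause-rule purpose, it points to Grade 3 or greater.

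**The case against.** The best reply is that this is a slip with little practical effect, because other text already leads the site to act. Much of that stands. Section 3.4.2 does oblige a call when a diary record shows relevant safety events, and its reference to the study period can be read generally, although it follows the text on the questionnaire used after Day 57. Section 3.4.8.4 treats every solicited reaction as caused by the injection, so a Grade 4 reaction may meet pause criterion 2 and be reportable to the Sponsor within 24 hours of observation. Judging whether there is another cause would ordinarily mean speaking to the participant. A Grade 3 reaction of another kind may also trigger the contact. Sites would very probably telephone about a fever above 40.0 °C in any case. None of this puts a time limit on the reactogenicity contact itself.

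A reader might go further in three ways that the documents do not support.

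- *That the wording delays contact until the scheduled diary review about a week after injection.* The 24-hour clock starts when the site becomes aware. If the site first sees a reading at that review, a Grade 3 fever waits just as long. The documents do not say when sites see diary entries, so the delay caused by the missing words cannot be computed.
- *That Grade 4 reactions go unrecorded or cannot reach a pause decision.* The eCRF rule and the Sponsor reporting duty both cover them.
- *That section 3.2.5 shows the intended wording for reactogenicity.* Its inclusive phrase applies to events other than reactogenicity, so it is not evidence here. The similar phrase in section 3.4.9 concerns vital signs.

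**Conclusion.** The point holds as a minor correction to a safety rule. Read literally, the contact trigger omits Grade 4 reactions other than rash. The practical gap is mainly 1 of the 12 solicited reactions, fever above 40.0 °C, and no other provision sets a timed reactogenicity contact for it. Confidence is high on the wording and much lower on any consequence. The documents give no rate of Grade 4 fever, and whether the illness-visit route in section 3.4.1 would catch such a fever depends on a symptom list they do not reproduce.

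The reach is limited. The SAP for Parts A and B (section 1) states that Part A is complete, and the pause rules bind only there. The correction therefore helps only if Part B or Part C injections remain to be given, a number the documents do not state. No endpoint, analysis set or estimate is affected. That Grade 3 or greater was intended is an inference from the eCRF rule and the purpose of the contact; nothing suggests that Grade 4 was left out on purpose.

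**What to change.** In Protocol section 3.4.8.4, change the first trigger to *Grade 3 or greater local or systemic ARs (Table 6)*. Leave the rash trigger as it is. The change can go into the next amendment or a clarification to sites while any injections remain. It is a change of a few words and adds no visits, staff or data collection.
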